Randomization to Letrozole vs. Anastrozole in Short Pubertal Males

NCT02137538

June 24, 2021

[name], Principal Investigator [name], Principal Investigator Stanford University Stanford, California 94305

Statistical Methods

Baseline auxologic and hormonal measures were summarized by treatment arm. Laboratory measures over time were presented as means with standard deviation, with key measures (total testosterone, estradiol, IGF-1) additionally displayed as boxplots by arm. Growth velocity (cm/year), height (cm), bone age (months), predicted adult height (cm), and DEXA z-scores over time were similarly visualized. Adverse events were listed by arm, and spinal film was assessed qualitatively.

To include all patients in an intent-to-treat approach, mixed effects linear regression was used to model each outcome as a function of treatment arm, indicators for follow-up timepoints, and their interaction for assessing effect modification of annual change by arm. Within-patient correlation was accounted for by a random effect. Estimated change since baseline with 95% confidence intervals were presented by arm if effect modification was deemed significant at the 0.05 alpha level and as an overall effect otherwise. All analyses were performed in the R statistical computing framework, version 4.0¹.

¹ R Core Team (2020). R: A language and environment for statistical computing. R Foundation for Statistical Computing, Vienna, Austria. URL https://www.R-project.org/

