2. STUDY PROCEDURES

a. Procedures

Patients from our endocrinology practice meeting our inclusion criteria will be consented into the study. They will be randomized into 1 of 2 treatment arms (Anastrozole 1 mg qday or Letrozole 2.5mg qday). Labs (gonadotropins, androgens, estrogens, growth factors, lipid profile) will be done every 6 months, bone age annually, and DEXA scans every 2 years.

We will see the patients annually until near final height (< 2 cm growth velocity per year), re-consenting in those over 18 years old. We will perform physical exams, obtain

anthropometric data, and repeat the above blood tests at least once off medication and perform imaging studies as warranted.

Beginning with this March 2016 renewal, we will no longer randomize to A vs L but use only A, continuing to collect observational data. **Procedure Risks**

We will be using the standard doses for the two drugs used. We will be monitoring with every 6 month physical exams and laboratory evaluation for possible side effects. At the discretion of the investigator, the medication may be reduced or discontinued, specifically if growth velocity falls below normal. **Use of Deception in the Study**

No deception will be used. Use of Audio and Video Recordings

No audio or video recording will occur. Alternative Procedures or Courses of Treatment

There are no alternatives to the above treatment. The only alternative would be to not start on the medication. Growth hormone is a theoretical option but is not standard of care for patients meeting these inclusion criteria. No standard treatment will be withheld. Will it be possible to continue the more (most) appropriate therapy for the participant(s) after the conclusion of the study?

Yes

g. Study Endpoint(s)

Our end point is final height which is defined as less than 2 cm of growth per year. We anticipate that all patients will reach this end point. **BACKGROUND**

a. Past Experimental and/or Clinical Findings

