Without estrogen action, the fusion of the growth plates is postponed and longitudinal growth continues. This is the basic idea behind using aromatase inhibitors to augment growth. Aromatase inhibitors block the conversion of testosterone to estrogen leading to more time for skeletal growth. Although aromatase inhibitors have been used widely as a treatment for estrogen responsive breast cancers and in fact there is a plethora of data in that population, to date there have been 3 published randomized control trials using third generation aromatase inhibitors, and only one has been published to final height. The study to final height showed an increase of 6 cm in comparison to controls. The other studies are ongoing, but preliminary data is promising with improvements of standard deviation scores for height from baseline as well as improvements in predicted adult height based on bone ages. Finally, the available short-term data for safety are reassuring, however long-term data is lacking. **Findings from Past Animal Experiments**

NA

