5. DRUGS, BIOLOGICS, REAGENTS, OR CHEMICALS USED IN THE STUDY

a. Investigational Drugs, Biologics, Reagents, or Chemicals

Investigational Product 1		
Name:	NA	
Dosage:	NA	
Administration Route:	NA	

b. Commercial Drugs, Biologics, Reagents, or Chemicals

Commercial Product 1		
Name:	Letrozole (no longer being used)	
Dosage:	2.5 mg	
Administration Route	Oral	
New and different use? (Y/N)	Yes	
Commercial Product 2		
Name:	Anastrozole	
Dosage:	1 mg	
Administration Route	Oral	
New and different use? (Y/N)	Yes	

6. **PARTICIPANT POPULATION**

a. Planned Enrollment

120; boys with short stature and/or growth hormone deficiency which may be congenital or acquired (post surgical or chemotherapy)

b. Age, Gender, and Ethnic Background

Males 10-17.99 years old, any ethnic background (identical to our clinical population) were recruited; those over 18 years old at f/u are reconsented,

c. Vulnerable Populations

The study is directed towards children because the purpose of the study is to evaluate growth. We will be monitoring for side effects closely.

d. Rationale for Exclusion of Certain Populations

All boys who fit under our inclusion criteria, regardless of ethnic background, will be included. Girls are excluded as aromatase inhibitor therapy will increase testosterone, causing untoward effects for girls.

e. Stanford Populations

None

f. Healthy Volunteers

None

g. Recruitment Details

The first person identifying patients for recruitment will be physicians in the Pediatric Endocrine Division at Lucile Packard. The protocol director will then continue the recruitment process in more detail.

h. Eligibility Criteria

i. Inclusion Criteria

Outpatient males with: Age 10-17.99 years; re-consented if over 18 years old at follow up Current height less than 5th percentile OR Predicted adult height (based on bone age) more than 10 cm below target height (mid parental height)

- Lab evidence of puberty: serum LH >0.3 IU/L and testosterone >15 ng/dl
- ii. Exclusion Criteria

Bone age xray more than 14 years FSH >20 IU/L

i. Screening Procedures

Pediatric endocrinologists will recruit all patients who qualify based on our inclusion criteria. Qualifying labs and bone age xray are usually obtained as part of routine clinical assessment of boys with short stature and/or delayed puberty, or would be obtained after enrollment and consent.

j. Participation in Multiple Protocols

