We will ask the patients about other studies they may be enrolled in although we do not anticipate that this will occur.

k. Payments to Participants

No payments

I. Costs to Participants

Clinic visits, drugs, and laboratory charges which are considered standard of care will be the patient's responsibility.

m. Planned Duration of the Study

We anticipate the average length of treatment to be 2-3 years. We will evaluate the patients every 6 months with laboratory evaluation with the same frequency. After treatment, follow-up visits will be scheduled annually until growth is completed, which will be on average an additional 3-4 years (6-7 years from start of treatment). Subjects will be re-consented upon reaching 18 years of age.

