7. RISKS

a. Potential Risks

i. Investigational devices

None

ii. Investigational drugs

None

iii. Commercially available drugs, biologics, reagents or chemicals

1) Arthralgia - reported in post-menopausal women at a frequency rate of 20-35%, lower in premenopausal women. Arthralgias have NOT been reported in the pediatric population.

2) Bone health - In adult women, there has been a reported decrease in bone mineral density by 6-7% after 5 years of therapy. We only have short-term data for young boys. Preliminary 1 year data did not show a difference in DEXA- measured bone mineral density in growth hormone (GH) deficient boys using Anastrozole in combination with GH. In boys with idiopathic short stature, there was no statistical difference between the treatment group using Letrozole versus the control group.

3) Fertility - In estrogen receptor knockout male mice, there is a progressive impairment of fertility. In one study using anastrozole in GH deficient boys, there was no difference in sperm parameters.

4) Metabolic parameters: lipids, insulin - In adult men with aromatase deficiency, increased cholesterol and increased insulin resistence has been descibed. In one study using Letrozole in pubertal boys, there was a significant decrease in HDL cholesterol, but all other lipids were unaffected. No changes have been reported in insulin sensitivity.5) Higher than normal testosterone levels could cause hair loss or behavioral changes. Neither has been reported in studies to date.

6) Growth velocity - excessive reduction in growth rate, which seems more likely to occur during the suppression of estrogen levels with Letrozole therapy. Procedures

Blood draws at each visit. Bone age annually. DEXA scan and lateral spine film at baseline and two years into the study. Radioisotopes/radiation-producing machines

DEXA scan which has less radiation than a standard chest XRAY; bone age and lateral spine x-ray. Physical well-being

Routine clinical history. Psychological well-being

Routine clinical history. Economic well-being

None

ix. Social well-being

None

x. Overall evaluation of risk

Medium International Research Risk Procedures

NA

c. Procedures to Minimize Risk

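### On-drug predicted adult height depends on bone age, so an arm difference in it can appear at equal attained heights and should not by itself carry a between-drug height claim.

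*SAP*

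**What the plan says.** The SAP (Statistical Methods) names the growth outcomes followed over time: "Growth velocity (cm/year), height (cm), bone age (months), predicted adult height (cm), and DEXA z-scores over time were similarly visualized". It then states that "mixed effects linear regression was used to model each outcome as a function of treatment arm, indicators for follow-up timepoints, and their interaction". It does not list the outcomes separately for the model, so the natural reading is that predicted adult height is among them. It names no prediction method, does not separate on-drug from off-drug predictions, and does not say how the outcome should be interpreted. It does not mention final or near-final height, although the protocol (2g Study Endpoints and 7d Study Conclusion) makes final height, defined as growth below 2 cm per year, the endpoint.

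Four places in the protocol bear on the prediction:

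- Inclusion Criteria (6h.i) tie it to bone age: "Predicted adult height (based on bone age) more than 10 cm below target height (mid parental height".
- Procedures (2a) set the schedule: "bone age annually, and DEXA scans every 2 years".
- Planned Duration (6m) says "We anticipate the average length of treatment to be 2-3 years", with follow-up afterwards of "on average an additional 3-4 years (6-7 years from start of treatment".
- Background gives the mechanism: "Without estrogen action, the fusion of the growth plates is postponed and longitudinal growth continues".

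The risk section (7a.iii) lists "excessive reduction in growth rate, which seems more likely to occur during the suppression of estrogen levels with Letrozole therapy".

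**The concern.** A prediction based on bone age has two inputs, the boy's height and his skeletal maturity. With annual bone ages and two to three years of treatment, about two or three follow-up predictions per boy fall on treatment. Drugs that postpone growth-plate fusion may well delay bone age too. If they do so to different degrees, predicted height will separate the arms even where measured height does not. Randomisation gives no protection, because the bone-age difference would arise after it.

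Predicted adult height is the SAP's listed outcome closest to the trial's own question, since the SAP does not name final height. A significant arm-by-time interaction in it could be read as a difference in adult height when it reflects, at least in part, a difference in bone age. Whether held-back bone age turns into centimetres is what follow-up to near-final height is meant to show.

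**Working it through.** The plan has no figure to reproduce. It gives no prediction formula, no bone-age difference between drugs, no standard deviations and no power calculation. What follows illustrates scale only.

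**Model (assumed).** Predicted height P = H / f, where H is current height and f is the fraction of adult height expected at the current bone age. Let s be the rise in f per bone-age year and d the between-arm difference in bone age, in years. At equal height the gap is H/(f − s·d) − H/f, which is close to d·H·s/f².

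**Inputs.** H, f, s and d are all assumptions. The only figure from the documents is the 6 cm gain over controls in the one earlier trial followed to final height (protocol, Background), used here as a yardstick.

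**Gap at equal height, d = 0.25 year**

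| Assumed set | Lowest corner | Highest corner |
|---|---|---|
| H 140–150 cm, f 0.84–0.92, s 0.02–0.04 | 140/(0.92 − 0.005) − 140/0.92 = 0.83 cm | 150/(0.84 − 0.01) − 150/0.84 = 2.15 cm |
| H 145–155 cm, f 0.86–0.90, s 0.03–0.05 | 0.25 × 145 × 0.03/0.90² = 0.25 × 5.37 = 1.34 cm | 0.25 × 155 × 0.05/0.86² = 0.25 × 10.48 = 2.62 cm |

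The second row uses the slope form; the exact difference at its top corner is 2.66 cm. Across both sets the gap is roughly 0.8 to 2.6 cm, or 14% to 44% of 6 cm (0.83/6 and 2.62/6). Under the first set it is 1.7–4.4 cm at d = 0.5 and 3.4–8.9 cm at d = 1.0.

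**Offset from slower growth.** P also falls when H falls, by 1/f (about 1.1 to 1.2 cm per cm of height). The height deficit that exactly cancels the gap is d·H·s/f:

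- first set: 0.25 × 140 × 0.02/0.92 = 0.76 cm, up to 0.25 × 150 × 0.04/0.84 = 1.79 cm;
- second set: 0.25 × 145 × 0.03/0.90 = 1.21 cm, up to 0.25 × 155 × 0.05/0.86 = 2.25 cm.

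So if the drug that delays bone age more also slows growth, the net direction in predicted height is not determined.

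**Chance of a significant result.** This comes from a simulation of a single-visit two-sample t-test with 60 boys per arm, both arms with the same height distribution (mean 145 cm, SD 6 cm), bone-age SD 0.8 year, f = 0.88 at the reference bone age and s from 0.02 to 0.04. Each setting had 3,000 runs.

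| Bone-age difference | p < 0.05 for predicted height | p < 0.05 for measured height |
|---|---|---|
| 0 | about 5% | about 5% |
| 0.25 year | 11–20% | about 5% |
| 0.5 year | 29–64% | about 5% |
| 1.0 year | 79–99% | about 5% |

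This is not the SAP's repeated-measures interaction test. Sixty per arm assumes that all 120 planned boys were randomised 1:1, an upper end because randomisation stopped at the March 2016 renewal (protocol 2a).

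**The case against.** Delayed maturation is how these drugs are meant to work. At equal height, a boy with a younger bone age may truly have more growth left, so a gap in predicted height may be partly or even largely real. This stands. A reader might infer that the whole gap is artefact; the documents do not support that, because nothing in them separates real remaining growth from prediction error.

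Both arms receive an aromatase inhibitor, and equal delay would largely cancel between them. This also stands. A reader might infer from the risk section that letrozole slows bone age more. That section speaks only of a greater likelihood of excessive growth-rate reduction and reports no bone-age difference between the drugs. Unequal delay is a possibility, not a finding.

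The SAP does not call predicted height primary or a surrogate for final height. It reports height, growth velocity and bone age beside it, so a careful reader could trace the source of a gap. It does not confine predictions to on-drug visits, and as f approaches 1 the prediction converges on attained height. These points limit the harm but do not remove it: the SAP gives no rule for reading the outcome and does not name the endpoint that would settle the matter.

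Finally, a comparison on near-final height is a completer analysis, whereas the mixed model was chosen to include everyone. That is a reason to add the comparison, not to substitute it.

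**Conclusion.** The point holds in conditional form. If the two drugs delay bone age unequally, on-drug predicted adult height can differ by arm at equal attained heights, and such a difference does not by itself show a difference in adult height. This rests on the protocol's statement that the prediction is based on bone age, on bone ages taken during treatment, and on the inference that drugs which postpone fusion may also delay bone age. The protocol does not state that last step in so many words.

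The size is illustrative: roughly 0.8 to 2.6 cm for an assumed 0.25-year bone-age difference, before any offset from slower growth. The documents give neither the difference nor the method. They do not show that such a gap would be wholly false, that it would favour letrozole, or that the mixed model should be dropped. This is a cheap improvement to analysis and interpretation.

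**What to change.** 1. Keep the all-patient mixed model as written.
2. Add a comparison, by randomised arm and among randomised boys only, of attained near-final height (growth below 2 cm per year). Express it as the difference from baseline pre-treatment predicted adult height, or adjust for that prediction. Make this the basis for any between-drug height claim. The baseline prediction cannot have been altered by the drugs.
3. Name the prediction method. Report on-drug predicted height as supportive, interpreted alongside bone age, and state that it is not evidence of a between-drug difference in adult height.
4. Report by arm the last on-drug prediction minus attained near-final height, which shows whether prediction error differs between drugs.
5. Report by arm the number and baseline features of boys without near-final height, and state how boys on letrozole when its use stopped (protocol 2a and 5b) are handled in the analysis. The documents do not say what happened to them.

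The cost is SAP wording and a few derived variables from data the protocol already plans to collect. The SAP is written in the past tense, but the additions can still be applied to the reporting. The real downside is that only boys reaching near-final height contribute. The protocol expects all of them to, but with growth completed on average six to seven years after starting treatment the loss may not be small, and no document gives the number who got there.

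### The SAP does not limit the anastrozole-versus-letrozole comparison to boys randomised before randomisation stopped in March 2016

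*SAP*

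**What the plan says.** Protocol section 2a describes the original design: "They will be randomized into 1 of 2 treatment arms", anastrozole or letrozole. The same section then says: "Beginning with this March 2016 renewal, we will no longer randomize to A vs L but use only A, continuing to collect observational data". The drug table in section 5b agrees, listing "Letrozole (no longer being used".

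The protocol's wording on recruitment points both ways. Section 6b uses the past tense (boys "were recruited; those over 18 years old at f/u are reconsented"). Section 6i uses the future tense: "Pediatric endocrinologists will recruit all patients who qualify based on our inclusion criteria". Neither is dated. Section 6a plans "120; boys with short stature and/or growth hormone deficiency", with no split by arm or by period.

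The SAP's Statistical Methods section, written more than five years after the change, says: "To include all patients in an intent-to-treat approach, mixed effects linear regression was used to model each outcome". The model terms are arm, follow-up timepoint indicators and their interaction, with a random effect for patient. If the interaction is significant at 0.05, changes from baseline are shown by arm; otherwise one overall change is shown. The SAP defines no analysis set, does not mention March 2016, and has no term for enrolment period or randomised status.

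**The concern.** The only arms the protocol defines are those created by randomisation. After March 2016 a boy starting treatment could receive only anastrozole. Under the SAP's wording he would be counted in the anastrozole arm with no randomised counterpart on letrozole. Any such contamination is one-sided and non-concurrent.

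The interaction test carries the between-drug conclusion, because it decides whether results appear by arm at all. If later boys are included, a difference between the two cohorts in change over time is reported as a drug difference under an intent-to-treat label. A constant difference in level is not a concern, because the interaction compares changes. The by-arm baseline summaries and adverse event listings would mix the cohorts as well.

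Later boys would also have shorter follow-up. From 1 March 2016 to 24 June 2021 is 5.31 years at most, whereas section 6m expects post-treatment follow-up of "on average an additional 3-4 years (6-7 years from start of treatment". They would therefore weigh more at early timepoints than at late ones.

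**Working it through.** **Reading the documents.** Section 2a stops randomisation but keeps anastrozole in use, which reads most naturally as a rule for boys still to start. Sections 6b and 6i conflict in tense and give no closing date. No SAP sentence excludes a boy who was never randomised. The omission is therefore certain; whether it affects any boy is not stated.

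**Size, if later boys exist.** The documents give no counts, SD, effect size or power, so there is no plan figure to reproduce. Every input below is an assumption except the 120, which is the planned enrolment in section 6a:

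- 120 boys analysed, randomised 1:1 before the change, no true drug difference.
- A share p enrolled later: n_N = 120p later boys, n_R = (120 − n_N)/2 per randomised arm.
- Baseline plus three annual visits, random intercept, SD of change = 1.
- Later boys differ from randomised anastrozole boys by d in change at every follow-up visit.

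Formulas:

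- Non-randomised share of the anastrozole arm: f = n_N/(n_R + n_N).
- Bias in the contrast: b = d × f.
- Standard error, all boys: se = √(1/n_R + 1/(n_R + n_N)).
- The three changes have covariance 0.5(I + J), so 1′Σ⁻¹1 = 3/(0.5 × 4) = 1.5. The noncentrality is 1.5 b²/se².
- Rejection rate: P(noncentral χ² on 3 df > 7.815).

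| p | n_R, n_N | f | se | b at d = 0.1, 0.3, 0.5 | Rejection at d = 0.1, 0.3, 0.5 |
|---|---|---|---|---|---|
| 0% | 60, 0 | 0% | 0.1826 | 0, 0, 0 | 5%, 5%, 5% |
| 10% | 54, 12 | 18% | 0.1835 | 0.02, 0.05, 0.09 | 5.1%, 5.8%, 7.3% |
| 25% | 45, 30 | 40% | 0.1886 | 0.04, 0.12, 0.20 | 5.4%, 8.8%, 16.8% |
| 40% | 36, 48 | 57% | 0.1992 | 0.06, 0.17, 0.29 | 5.7%, 12.4%, 28.2% |

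Worked case, p = 25%, d = 0.3: f = 30/75 = 0.40; b = 0.12; noncentrality = 1.5 × 0.0144/0.03556 = 0.607; rejection 8.8%.

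**Simulation.** With 20,000 runs and an F test, the rates for p = 10%, 25%, 40% are 5.0%, 4.8%, 5.0% at d = 0; 5.6%, 8.6%, 11.8% at d = 0.3; and 7.1%, 15.5%, 27.0% at d = 0.5. The closed form is about one percentage point too high at the upper end.

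**Unequal follow-up.** Generalised least squares with randomised boys seen in years 0–6, later boys in years 0–5, intraclass correlation 0.5 and a joint 6-df test gives 5.6%, 7.9% and 10.6% for a 0.3 SD difference in change. A 0.3 SD constant level difference gives at most 5.1%; with equal follow-up it gives exactly 5%.

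**The case against.** The strongest reply is that the triggering fact is not shown. No sentence says a boy enrolled after March 2016, and section 6b together with the talk of continuing observation fits follow-up of boys already enrolled. The future tense in section 6i is weak evidence, because section 2a also keeps its future-tense randomisation sentence alongside the statement that randomisation has ended. The SAP's title and its intent-to-treat label suggest randomised boys, and a boy who was never randomised has, strictly, no arm. The SAP sentence may only explain why a mixed model was chosen, namely to keep boys with incomplete follow-up. The magnitudes rest wholly on assumptions, and at a 0.1 SD cohort difference the test is practically nominal.

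Much of this stands. A benign reading is possible, the effect may be nil, and the follow-up scenario is stylised. But a title and a label do not define an analysis set, and the label is attached to all patients in a study that had both a randomised phase and an anastrozole-only phase. Nothing in the documents shows that enrolment closed before the change. Because the protocol leaves the matter open, the SAP needs to settle it.

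**Conclusion.** The concern holds and should be fixed. It is certain that the SAP does not restrict the comparison to boys randomised before March 2016. Followed literally, its rule would admit later, non-randomised boys to the anastrozole arm of the test that decides the between-drug conclusion.

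The consequence is conditional: nil if no boy first enrolled after the change, and material if a quarter or more did and the cohorts differ by 0.3 SD or more in change (rejection 8.8% or higher in closed form, 8.6% or higher by simulation). The documents favour no value for the later share or the cohort difference, so the size cannot be narrowed further.

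**What to change.** State in the SAP, or in a dated addendum since it is written in the past tense, that every anastrozole-versus-letrozole comparison (interaction tests, by-arm changes, adverse events) uses only boys randomised before the March 2016 change, analysed as randomised. Describe any boys given anastrozole without randomisation as a separate observational cohort. Report the numbers randomised, enrolled after the change, and moved off letrozole, if any. If later boys were in the fitted models, rerun the contrast without them. If there were none, say so in one sentence.

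The work is a few sentences and one filter on randomisation status, with no loss if nobody enrolled later. Otherwise precision falls. The restricted standard error is √(2/n_R), and power is for a true 0.5 SD drug difference with no cohort difference:

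| Later share | Restricted se (ratio to all boys) | Power, all boys | Power, randomised only | Break-even d |
|---|---|---|---|---|
| 10% | 0.1925 (1.049) | 80.9% | 76.7% | 0.32 |
| 25% | 0.2108 (1.118) | 78.5% | 68.0% | 0.24 |
| 40% | 0.2357 (1.183) | 73.5% | 57.2% | 0.22 |

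Intervals for the contrast are thus about 5%, 12% or 18% wider. Break-even d is √(se_R² − se²)/f, where se_R is the restricted standard error; below it, the all-patient estimate has the smaller mean squared error. The case for the restriction is therefore a valid randomised comparison, not precision. The all-patient model can be kept as a labelled sensitivity analysis.

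### The SAP model leaves out bone age at entry and its interaction with time, which costs precision in the arm-by-timepoint test; the randomised comparison itself is not biased by this

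*SAP*

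**What the plan says.** The SAP (Statistical Methods) states that "mixed effects linear regression was used to model each outcome as a function of treatment arm, indicators for follow-up timepoints, and their interaction". Within-patient correlation is handled by a random effect whose form is not given. Baseline measures are summarised by arm but do not enter the model. Change since baseline is reported by arm if the interaction is significant at 0.05, and as a single overall effect otherwise.

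On who enters, Protocol section 6b says "Males 10-17.99 years old, any ethnic background (identical to our clinical population) were recruited". Section 6h excludes boys with "Bone age xray more than 14 years", gives no lower limit for bone age, and requires "Lab evidence of puberty: serum LH >0.3 IU/L and testosterone >15 ng/dl". Section 6i indicates that the bone-age film is taken in routine assessment or, failing that, after consent, so a baseline value should exist for every boy.

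On allocation, Protocol section 2a says "They will be randomized into 1 of 2 treatment arms (Anastrozole 1 mg qday or Letrozole 2.5mg qday". No stratification is described. The same section ends randomisation at the March 2016 renewal, with anastrozole alone used from then on and observational data still collected. Planned enrolment is 120 (section 6a); the number randomised is not stated.

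**The concern.** The protocol's background section rests the treatment on delaying growth-plate fusion, so that growth goes on for longer. Section 6h also takes predicted adult height from bone age. By the protocol's own reasoning, then, bone age at entry predicts how much a boy will still grow on either drug.

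A model without it treats that predictable variation as noise in the drug contrast. This affects what is reported, because a missed interaction leads to one overall estimate for both drugs, while the stated purpose of the study is to find out whether they differ. A chance difference between the arms in maturity would also go unadjusted.

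**Working it through.** The documents give no effect size, standard deviation or power figure, so there is nothing to reproduce. The results below rest on the stated assumptions.

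**1. Which term matters.** Write the SAP model as Y(i,t) = μ + α·arm + τ(t) + δ(t)·arm + b(i) + e(i,t), taking the random effect b(i) as an intercept. In the change from baseline b(i) cancels, so stable differences in level are already dealt with. A main effect γ·BA(i) cancels in the same way. Only λ(t)·BA(i), bone age by timepoint, removes maturity-driven differences in growth from δ(t). In simulated trials with complete data (40 boys per arm, baseline and three annual visits, growth-slope SD 1.5 cm/year, 60 runs per setting), adding maturity as a main effect changed the year-3 arm-by-time estimate by less than 3×10⁻¹³ cm.

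**2. Precision.** Let R² be the share of the variance in change explained by baseline bone age, assumed 20–50%. The standard error is multiplied by √(1 − R²):
- R² = 0.20: √0.80 = 0.89, a cut of about 11%
- R² = 0.35: √0.65 = 0.81, a cut of about 19%
- R² = 0.50: √0.50 = 0.71, a cut of about 29%

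**3. Power.** Assume a true drug difference of 0.5 SD in change at one visit and two-sided alpha 0.05 (the SAP does not state sidedness). Power = Φ(0.5 / [√(2/n)·√(1 − r²)] − 1.96), where r is the correlation of baseline maturity with growth.

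| Boys per arm | Unadjusted | r = 0.5 (R² = 0.25) | r = 0.7 (R² = 0.49) |
|---|---|---|---|
| 30 | 49% | 61% | 77% |
| 60 | 78% | 89% | 97% |

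Sixty per arm is the planned 120 split equally; 30 allows for randomisation having stopped early. The SAP's interaction test covers several timepoints, so these figures show direction and rough size only.

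**4. Bias among randomised boys.** With 60 per arm, no drug effect, r = 0.3, 0.5 and 0.7, and 4,000 runs each, the mean unadjusted estimate lay between −0.006 and 0.004 SD and the type I error between 5.1% and 5.7%. There is no bias.

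**5. Chance imbalance.** The arm difference in mean maturity has SD √(2/n) in units of the maturity SD. Its 95% range is ±1.96·√(2/60) = ±0.36 SD with 60 per arm and ±1.96·√(2/30) = ±0.51 SD with 30.

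**6. Pooling later boys.** Assume 40 randomised boys per arm plus 40 non-randomised anastrozole boys who are 0.5 SD more mature. Half of the anastrozole group is then shifted, so its mean maturity moves by 0.25 SD and the expected bias is −0.25·r, that is −0.075, −0.125 and −0.175 SD at r = 0.3, 0.5 and 0.7. Simulation gave −0.07, −0.12 and −0.17 SD, with type I error 6.9%, 9.6% and 13.9%. Adjustment brought the bias to about zero and the type I error to 4.5–5.6%. Without a maturity shift there was no bias.

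**The case against.** The strongest reply is that an unadjusted comparison of randomised arms is valid. That stands: step 4 confirms it. A reader might infer from the wide eligibility range that the drug comparison is biased, but the documents do not support this. Wide eligibility adds variance, and chance imbalance is part of the sampling variation that a correct confidence interval already covers. One proviso is that the interval be correct, which depends on the unstated form of the random effect and is a separate question.

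A reader might also turn an imbalance in bone age into centimetres and set it against the 6 cm gain in the protocol's background section. That does not work either. The documents give no growth per year of bone age, the SAP model estimates change at visits and not total remaining growth, and the 6 cm is a difference from controls, not between two drugs.

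The spread in maturity is also narrower than an eight-year age range suggests, because bone age is capped at 14 and the puberty criterion trims the immature end. Predicted adult height already uses bone age, so there is less to gain there. Finally, the SAP is written in the past tense, so a covariate added now may be a post hoc choice.

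These points limit the size and scope of the concern. They do not remove the loss of precision for height and growth velocity, and a summary of baseline measures by arm shows an imbalance without adjusting for it.

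**Conclusion.** The point holds as a matter of precision. The model omits a prognostic value that the protocol already collects, and the cost falls on the test that decides whether drug-specific results appear. If baseline bone age explains 20–50% of the variance in change, adjustment would cut the standard error by about 11–29%. That range is an assumption, and if bone age explains less, the gain is smaller.

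The randomised comparison is not biased by the omission. Bias could arise if boys given anastrozole without randomisation after March 2016 are pooled and differ in maturity. The SAP says that all patients are included but not how such boys are handled, and the documents give neither their number nor their maturity, so step 6 is only an illustration. The gain is smaller for predicted adult height and has not been quantified for sex steroids.

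**What to change.** In the SAP, add baseline bone age, centred at its mean, and its interaction with the timepoint indicators to the models for height and growth velocity. State that the interaction is required, since a main effect alone does not alter the arm-by-timepoint contrast.

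Where bone age is itself the outcome, use its baseline value as the covariate and only the follow-up visits as outcomes. The drug comparison there is the arm term together with arm by timepoint, not the interaction alone.

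State also whether boys treated after March 2016 without randomisation enter the drug comparison. Adjusting for bone age would not correct other differences between them and the randomised boys.

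No new data are needed. The cost per height or growth-velocity model is one parameter plus one for each follow-up timepoint: 1 + 3 = 4 with three annual visits, 1 + 7 = 8 with seven. If results have already been seen, keep the existing model as specified and label the adjusted one as added later.
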